2 SYNOPSIS

Title of Study:	A Multi-center, Randomized, Double-blind, Placebo-controlled, Parallel Group, Phase 2a Study to Assess the Efficacy and Safety of ME3183 Administered Orally in Subjects with Moderate to Severe Plaque Psoriasis
Protocol Number:	ME3183-3
Investigators/Study Sites:	Approximately 30 study sites across the United States and Canada will participate in this study.
Phase of Development:	Phase 2a
Objectives:	
Primary Objective
 
To evaluate the efficacy of oral ME3183 compared with placebo at Week 16 in subjects with moderate to severe plaque psoriasis as measured by the Psoriasis Area and Severity Index (PASI) score 
Secondary Objectives
 
To evaluate the safety and tolerability of oral ME3183 in subjects with moderate to severe plaque psoriasisTo evaluate the efficacy of oral ME3183 in subjects with moderate to severe plaque psoriasis at various time pointsTo evaluate the effect of oral ME3183 on patient-reported outcome (PRO) measures in subjects with moderate to severe plaque psoriasisTo evaluate the pharmacokinetics (PK) of ME3183 and its metabolite (CCI [REDACTED]) in subjects with moderate to severe plaque psoriasis who are treated with oral ME3183 
Exploratory Objectives
 
CCI [REDACTED]

Study Endpoints:	
Primary Endpoint
 
The primary efficacy endpoint is the proportion of subjects achieving $\geq 75\%$ reduction from Baseline in the PASI score (PASI-75) at Week 16.
 
Secondary Endpoints
 
Safety Endpoints
 
The safety endpoints are as follows:
 
The incidence, severity, and seriousness of adverse events (AEs) reported over the 16-week Treatment Period and the 4-week Follow-up PeriodChanges from Baseline in clinically significant (CS) physical examination findings and vital sign measurements (blood pressure, heart rate, respiratory rate, body temperature, and body weight) over the 16-week Treatment Period and the 4-week Follow-up PeriodChanges from Baseline in electrocardiogram (ECG) findings over the 16-week Treatment Period and the 4-week Follow-up PeriodChanges from Baseline in safety laboratory values (hematology, coagulation,

	
blood chemistry, and urinalysis) over the 16-week Treatment Period and the 4-week Follow-up Period
 
Efficacy Endpoints
 
The secondary efficacy endpoints are as follows:
 
• The percent change from Baseline in PASI score at all visits from Week 1 to Week 16• The proportion of subjects achieving PASI-50, PASI-75, PASI-90, PASI-100 at all visits from Week 1 to Week 16• Time to PASI-50 and PASI-75• The proportion of subjects achieving a Static Physicians Global Assessment (sPGA) score of "0" ("clear") or "1" ("almost clear") combined with 2-point reduction on the 5-point sPGA scale at all visits from Week 1 to Week 16• The change from Baseline in affected body surface area (BSA) at all visits from Week 1 to Week 16• The change from Baseline in the itch numerical rating scale (NRS) at all visits from Week 1 to Week 16• The change from Baseline in the Dermatology Life Quality Index (DLQI) score at all visits from Week 1 to Week 16• Percentage of subjects with at least a 5-point reduction from Baseline in the DLQI score at all visits from Week 1 to Week 16 
Pharmacokinetic Endpoint
 
The PK endpoint is the trough plasma concentration of ME3183 and its metabolite (CCl [REDACTED]).
 
Exploratory Endpoints
 
CCl [REDACTED]

Study Design:	
This multi-center, randomized, double-blind, placebo-controlled, parallel group, Phase 2a study is designed to assess the efficacy and safety of ME3183 administered orally in subjects with moderate to severe plaque psoriasis. The study consists of a 4-week Screening Period (Day -28 to Day -1), a 16-week double-blind Treatment Period (Day 1 to Day 113), and a 4-week Follow-up Period (Day 114 to Day 141). The total duration of study participation for each subject is approximately 24 weeks.
 
Note: The study drug is administered from Day 1 to Day 112 in the Treatment Period and the end of Treatment Period assessments will be performed on Day 113.
 
The duration of the Follow-up Period is from Day 114 to Day 141 and the end of

	
Follow-up Period assessments will be performed on Day 141.
 
After the Screening Period, approximately 125 eligible subjects with a confirmed diagnosis of psoriatic plaques, a BSA involvement of $\geq 10\%$ (at Screening and Baseline), a PASI score 12 to 40 (at Screening and Baseline), and an sPGA ≥ 3 (at Screening and Baseline) will be randomly assigned to receive ME3183 [] mg twice daily [BID], [] mg once daily [QD], [] mg BID, or [] mg QD) or placebo in a 1:1:1:1 ratio. To promote balanced allocation, randomization will be stratified by the subject's receipt (yes/no) of previous treatment with a biologic drug for psoriasis. Bio-naïve subjects will be randomized above 50% of the planned total subject randomization.
 
After randomization (Day 1), all subjects will be evaluated at Baseline and at Weeks 1, 2, 4, 8, 12, 16, and 20. Efficacy assessments (ie, PASI, BSA, sPGA, and PRO assessments [DLQI and the itch NRS]), will be assessed at Baseline (Day 1) and at Weeks 1, 2, 4, 8, 12, 16, and 20. Blood samples for PK assessment will be collected predose at Weeks 1, 4, 8 and 16. Blood samples for [] assessments will be collected predose at Baseline (Day 1), Weeks 4 and 16. Safety and tolerability will be assessed by physical exam, monitoring for AEs and serious AE (SAEs), demographics, medical history, vital signs and safety laboratory tests (hematology, coagulation, blood chemistry, and urinalysis) at Baseline (Day 1) and Weeks 1, 2, 4, 8, 12, 16, and 20. ECGs will be assessed at Baseline (Day 1) and Weeks 4, 8, 12, 16, and 20.

Selection of Subjects:	Inclusion Criteria: 
1. Subject is willing and able to participate in the study and has read, understood, and signed the informed consent form according to national regulations.2. Subject is a male or female aged 18 to 75 years (inclusive) at the time of consent (ie, Screening).3. Subject has a body mass index ≥ 18.5 to $< 40 \text{ kg/m}^2$ at Screening.4. Subject has a diagnosis of plaque psoriasis for ≥ 24 weeks prior to Screening.5. The subject's symptoms of plaque psoriasis are stable in the opinion of the investigator. Stable is defined as no acute deterioration (eg, pustulation or erythroderma) within 12 weeks before Screening and no rebound of plaque psoriasis within 4 weeks before Screening.6. The subject's severity of disease meets all of the following criteria:
• Psoriatic plaques must cover $\geq 10\%$ of BSA at Screening and Baseline• PASI score 12 to 40 at Screening and Baseline• sPGA ≥ 3 at Screening and Baseline7. Subject is deemed by investigator to be eligible for phototherapy or systemic therapy.8. Subject agrees to avoid prolonged exposure to sunlight or use of artificial sunbathing (eg, tanning booths) or other ultraviolet light sources during the Treatment Period.9. Subject, if female and of childbearing potential, must have a negative serum pregnancy test at Screening and negative urine pregnancy test at Baseline. Any women of childbearing potential (WOCBP) must agree to sexual abstinence or to use a highly effective contraceptive measure starting at Screening, continuing throughout the entire Treatment Period, and for at least 4 weeks after taking the last dose of study treatment. A female subject is considered to be a WOCBP after menarche and until she is in a postmenopausal state for 12 months or otherwise permanently sterile (for which acceptable methods include hysterectomy, bilateral salpingectomy,

and bilateral oophorectomy).

10. Subject, if a fertile male, agrees to sexual abstinence or to use a condom during sexual activity with their female partner of childbearing potential starting at Screening, continuing throughout the entire Treatment Period, and for at least 4 weeks after taking the last dose of study treatment. A male subject is considered fertile after puberty unless permanently sterile by bilateral orchidectomy. Additionally, if their partner is a WOCBP, then their partner should be advised to use a highly effective contraceptive measure during sexual activity starting at Screening, continuing throughout the entire Treatment Period, and for at least 4 weeks after taking the last dose of study treatment.
11. Subject, if female, must agree to not donate, or retrieve for her own use, ova starting at Screening, continuing throughout the entire Treatment Period, and for at least 4 weeks after taking the last dose of study treatment.
12. Subject, if male, must agree to not freeze or donate sperm starting at Screening, continuing throughout the entire Treatment Period, and for at least 4 weeks after taking the last dose of study treatment.

Exclusion Criteria:

1. Subject has a diagnosis of non-plaque psoriasis (predominantly guttate, pustular, inverse, or erythrodermic) or drug-induced psoriasis.
2. Subject has any unstable or CS (as determined by the investigator) cardiac, endocrinologic, gastroenterologic, pulmonary, neurologic, psychiatric (such as major depression), hepatic, renal, hematologic, immunologic disease, or other disease (eg, uncontrolled diabetes) that would place the subject at unacceptable risk if they were to participate in the study.
3. Subject has suicidal ideation or behavior in the past 12 months as indicated by a positive response (yes) to questions 3, 4, or 5 on the Columbia-Suicide Severity Rating Scale completed at Screening and/or at Baseline.
4. Subject has a present recurrent medical condition associated with significant gastrointestinal events (eg, nausea, vomiting, constipation, abdominal pain, diarrhea).
5. Subject has any condition that would confound the ability to interpret data from the study (eg, eczema, atopic dermatitis, lupus, inflammatory bowel disease).
6. Subject has any degree of dysphagia that may interfere with the oral dosing of the study treatment.
7. Subject has a history of allergy or hypersensitivity to any component of the study treatments.
8. Subjects who have had a prior laboratory confirmed COVID-19 test or have been in close physical contact (6 feet or closer for at least 15 minutes) with a person who is known to have laboratory confirmed COVID-19 or with anyone who has any symptoms consistent with COVID-19 within the past 14 days at Screening or Baseline.
9. Subjects experiencing any of the following symptoms at Screening or Baseline:
 - Fever or chills
 - Cough
 - Shortness of breath or difficulty breathing
 - Fatigue
 - Muscle or body aches
 - Headache
 - New loss of taste or smell
 - Sore throat

	
• Congestion or runny nose• Nausea or vomiting• Diarrhea 
10. Subject has active or chronic hepatitis B virus or hepatitis C virus (HCV) infection as per Screening viral serology tests. Exception: If the subject has received documented treatment which was curative for HCV and tests negative for HCV RNA at Screening, the subject may be considered for randomization.
 
11. Subject is positive for the HIV antibodies (HIV-1 or HIV-2) at Screening or has a history of congenital or acquired immunodeficiency (eg, common variable immunodeficiency disease).
 
12. Subject has a recent history of drug, substance, or alcohol abuse/dependence within 1 year prior to Screening as determined by the investigator.
 
13. Subject has an active infection (bacteria, viral, fungal, etc.) requiring treatment with systemic antibiotics within 4 weeks of Screening. Any treatment for such infections must be completed at least 4 weeks prior to Screening.
 
14. Subject has active tuberculosis or history of incompletely treated tuberculosis per medical history.
 
15. Subject has a malignancy or history of malignancy (except for treated [ie, cured] basal cell or squamous cell in situ skin carcinomas and treated [ie, cured] cervical intraepithelial neoplasia or carcinoma in situ of the cervix with no evidence of recurrence).
 
16. Subject is pregnant or breastfeeding at Screening or at Baseline.
 
17. Subject has a history of lack of efficacy (inadequate efficacy when used in adequate dose and duration in accordance with the approved label) to any biological products for psoriasis.
 
18. Subject has received 2 or more biological products in the past for the treatment of psoriasis.
 
19. Subject has a history of lack of efficacy to 2 or more non-biologic systemic therapy due to inadequate efficacy when administered in adequate dose and duration in accordance with their label (approved in the subject's country) for psoriasis.
 
20. Subject has received any prior treatment with apremilast or any other phosphodiesterase 4 inhibitor.
 
21. Subject has received ustekinumab, secukinumab, brodalumab, ixekizumab, guselkumab, risankizumab, tildrakizumab, or briakinumab (or any other therapeutic agent targeting IL-12, IL-17, or IL-23) within 24 weeks of first administration of study treatment.
 
22. Subject has received TNF-α inhibitor(s)/blocker(s) within 8 weeks of first administration of study treatment.
 
23. Subject has received natalizumab (an integrin receptor antagonist), or agents that modulate B cells or T cells (eg, alemtuzumab, abatacept, alefacept) within 12 weeks of first administration of study treatment.
 
24. Subject has received rituximab within 24 weeks of first administration of study treatment.
 
25. Subject has received any systemic immunosuppressants (eg, methotrexate, azathioprine, cyclosporine, 6-thioguanine, mercaptopurine, mycophenolate mofetil, hydroxyurea, tacrolimus), any protein kinase inhibitor (eg, tofacitinib, baricitinib, peficitinib, upadacitinib), or anakinra within 4 weeks of the first administration of study treatment.
 
26. Subject has received phototherapy (e g, ultraviolet B including narrow band ultraviolet B, Goeckerman therapy, and excimer laser or psoralen ultraviolet A) or any systemic medications/treatments that could affect psoriasis or sPGA evaluation (including, but not limited to, oral or injectable corticosteroids, retinoids, 1,25-dihydroxy vitamin D3 and analogues,

--	--

	
psoralens, sulfasalazine, or fumaric acid derivatives) within 4 weeks of the first administration of study treatment.
 
27. Subject has had a recent initiation of a drug that is known to potentially cause or exacerbate psoriasis (including, but not limited to, beta-blockers, lithium, and anti-malarials) within the 8 weeks prior to the first administration of study treatment; a subject who has been on a stable dose for at least 8 weeks prior to the first administration of study treatment without exacerbation of psoriasis may be randomized and does not need to discontinue these medications.
 
28. Subject has used topical medications/treatments that could affect psoriasis or sPGA evaluation (including, but not limited to, certain corticosteroids, anthralin, calcipotriene, topical vitamin D derivatives, retinoids, tazarotene, methoxsalen, trimethylpsoralen, pimecrolimus, tacrolimus, or phosphodiesterase 4 inhibitor) within 2 weeks of the first administration of study treatment.
 
29. Subject has received an investigational drug for biologic therapy within the previous 24 weeks prior to the first administration of study treatment or received any other non-biologic investigational therapy/drugs or device within 4 weeks or 5 half-lives (whichever is longer) prior to the first administration of study treatment.
 
30. Subject has received any prior treatment with ME3183.
 
31. Subject has any of the following abnormal laboratory test findings at Screening.
 
• Abnormal hepatic function
◦ Aspartate aminotransaminase or alanine aminotransaminase $\geq 2 \times$ upper limit of normal or◦ Total bilirubin $\geq 2 \times$ upper limit of normal, unless the subject has a diagnosis of Gilbert's syndrome• White blood cell count $< 3000/\text{mm}^3$ ($< 3.0 \times 10^9/\text{L}$)• Neutrophil count $< 1000/\text{mm}^3$ ($< 1.0 \times 10^9/\text{L}$)• Platelet count $< 100,000/\mu\text{L}$ ($< 100 \times 10^9/\text{L}$)• Hemoglobin $< 8.0 \text{ g/dL}$• Creatinine clearance estimated by Cockcroft-Gault formula $< 60 \text{ mL/min}$• Hemoglobin A1c $> 9.0\%$ 
32. Subject has a CS abnormality on a 12-lead ECG or corrected QTcF $> 450 \text{ msec}$ at Screening or Baseline.
 
33. Subject has a systolic blood pressure $\geq 160 \text{ mmHg}$ or a diastolic blood pressure $\geq 100 \text{ mmHg}$ (based on at least 2 repeat measurements) at Screening.
 
34. Prisoners or subjects who are incarcerated for any reason.
 
35. Subject has any other factor constituting disqualification for study inclusion in the judgement of the investigator.

Planned Sample Size:	
Approximately 125 eligible subjects are planned to be randomized (25 subjects per treatment group). Eligible subjects will be centrally randomized in a 1:1:1:1:1 ratio to 1 of the following treatment groups:
 
• Treatment Group 1: [REDACTED] mg ME3183 BID administered orally): [REDACTED] capsule of [REDACTED] mg ME3183 and [REDACTED] capsules of matching placebo in the morning and evening• Treatment Group 2: [REDACTED] mg ME3183 QD administered orally): [REDACTED] capsules of [REDACTED] mg ME3183 and [REDACTED] capsule of matching placebo in the morning and [REDACTED] capsules of matching placebo in the evening• Treatment Group 3: [REDACTED] mg ME3183 BID administered orally): [REDACTED] capsule of [REDACTED] mg ME3183 and [REDACTED] capsule of [REDACTED] mg ME3183 and [REDACTED] capsule

	
of matching placebo in the morning and evening
 
• Treatment Group 4: (█ mg ME3183 QD administered orally): █ capsules of █ mg ME3183 in the morning and █ capsules of matching placebo in the evening• Treatment Group 5 (Placebo BID administered orally): █ capsules of matching placebo in the morning and evening 
To promote balanced allocation, randomization will be stratified by subject's receipt (yes/no) of previous treatment with a biologic drug for psoriasis. Each treatment group will include randomized subjects who 1) are bio-naïve and 2) received previous treatment with a biologic drug for psoriasis. After randomization of subjects has reached the maximum percentage as determined by the sponsor for subjects that have received previous treatment with a biologic drug for psoriasis, randomization in this group will be stopped and the study sites will be informed accordingly.

Study Treatments	ME3183 (█ mg, █ mg, █ mg, and █ mg) and matching placebo will be prepared using the following ME3183 and placebo capsules: 
• ME3183 Capsule █ mg• ME3183 Capsule █ mg• ME3183 Placebo Capsule
Treatment Duration:	The treatment duration for an individual subject will be 16 weeks. Each subject will receive BID treatment under fed condition (within approximately 30 minutes after a standard meal) from Day 1 to Day 112.
Efficacy:	Efficacy assessments (including PRO assessments) will include: 
• PASI score• BSA• sPGA• Itch NRS• DLQI
Safety:	Safety assessments will include: 
• AE/ SAEs• 12-lead ECGs• Physical examinations (complete/targeted) including height and body mass index• Vital signs
◦ Blood pressure (systolic and diastolic)◦ Heart rate◦ Respiratory rate◦ Body temperature◦ Body weight• Safety laboratory tests including:
◦ Viral serology (hepatitis B virus, HCV, and HIV)◦ Hematology and coagulation◦ Blood chemistry◦ Urinalysis◦ Pregnancy tests (WOCBP only; serum or urine β-human chorionic gonadotropin)◦ Serum follicle-stimulating hormone (postmenopausal women only)

Pharmacokinetics:	Blood samples for the determination of the concentrations of ME3183 and its metabolite (CCI [REDACTED]) will be collected from each subject in each treatment group. The PK blood samples will be taken predose at scheduled visits until Week 16.
CCI	
Other Assessments:	
Other assessments will include:
 
• Eligibility assessments: Informed consent• Inclusion/exclusion criteria• Dermatologic and medical history• History of previous treatment with a biologic drug for psoriasis• Columbia-Suicide Severity Rating Scale• Demographics• Prior and concomitant medications/therapies or procedures• Treatment compliance• Medical photography of the target skin lesion (at selected sites in a selected number of subjects for documentation and publication purposes only)
Statistical Methods and Planned Analyses:	
Determination of Sample Size
 
No formal sample size calculation was performed.
 
For the assessment of efficacy and safety of ME3183 in subjects with moderate to severe plaque psoriasis in this proof-of-concept study, approximately 125 eligible subjects will be enrolled. Twenty-five subjects will be randomized to each of the following treatment groups: ME3183 [REDACTED] mg BID, ME3183 [REDACTED] mg QD, ME3183 [REDACTED] mg BID; ME3183 [REDACTED] mg QD, and placebo. The number of planned subjects is considered adequate to assess safety and to provide efficacy estimates for in this Phase 2a study. The expected drop-out rate is assumed to be 10%.
 
Analysis Sets
 
Full Analysis Set
 
All subjects who have been randomized, received at least 1 dose of study drug, and have at least 1 evaluable post-Baseline time point for primary endpoint will be included in the full analysis set (FAS). Analyses in the FAS will be based on the subject's randomized treatment group.
 
Per Protocol Set
 
The per protocol set (PPS) is a subset of the FAS; the PPS will exclude subjects with protocol deviations that may significantly impact the assessment of the primary objective of the study. Analyses in the PPS will be based on the study treatment actually received by each subject. All decisions to exclude subjects from the PPS will be made prior to the unblinding of the study.
 
Safety Analysis Set
 
All randomized subjects who received at least 1 dose of study drug will be included in the safety analysis set. Analyses in the safety analysis set will be based on the study treatment actually received by each subject.
 
Pharmacokinetic Analysis Set
 
The PK analysis set will consist of all subjects who were correctly administered at

	
least 1 ME3183 dose and where ME3183 or CCI concentration data is available without any protocol deviation interfering with these results. Analyses in the PK analysis set will be based on the study treatment actually received by each subject.
 
CCI

	
Statistical Analyses
 
Efficacy Analyses
 
Unless otherwise specified, all efficacy analyses will be performed using the FAS. The analysis of the primary efficacy endpoint will also be performed using the PPS.
 
Analysis of the Primary Efficacy Endpoint
 
The primary efficacy endpoint is the proportion of subjects achieving $\geq 75\%$ reduction from Baseline in the PASI score at Week 16. For each ME3183 treatment group, the difference in the proportion of subjects achieving the difference in PASI-75 (ME3183 – placebo) and its 95% confidence interval will be estimated and tested for superior treatment effect using the Cochran-Mantel-Haenszel test at a 1-sided significance level of $\alpha = 0.025$. The PASI score will be reported for each treatment group together with the 95% confidence interval for mean.
 
Analyses of the Secondary Efficacy Endpoints
 
The proportion of subjects achieving PASI-50, PASI-75, PASI-90, and PASI-100, the proportion of subjects with an sPGA score of “0” or “1” combined with 2-point reduction on the 5-point sPGA scale, and the proportion of subjects with at least a 5-point reduction from Baseline in the DLQI score will be analyzed similar to the primary endpoint analysis.
 
The proportion of subjects achieving PASI-50, PASI-75, PASI-90, and PASI-100, the proportion of subjects with an sPGA score of “0” or “1” combined with 2-point reduction on the 5-point sPGA scale, and the proportion of subjects with at least a 5-point reduction from Baseline in the DLQI score will be summarized by treatment group and visit. The percent change from Baseline in PASI score and change from Baseline in affected BSA, the itch NRS, and the DLQI score will be summarized by treatment group and visit. The percent change from Baseline in PASI score and the change from Baseline in the affected BSA, the DLQI score, and the itch NRS will be analyzed using a mixed-effect model for repeated measures when applicable.
 
Kaplan-Meier estimate will be used for summarizing the time to PASI-50 and PASI-75. The log-rank test may be used for comparing the time to PASI-50 and PASI-75 between each ME3183 treatment group and placebo. The Cox proportional hazard model may also be used for analyzing the time to PASI-50

and PASI-75. The time to PASI-50 and PASI-75 will be summarized by treatment group.

Analyses of the Exploratory Efficacy Endpoints

CCI

Safety Analyses

All safety analyses will be performed using the safety analysis set. All recorded AE and SAEs will be listed and tabulated by Medical Dictionary for Regulatory Activities (version 24.1 or higher) system organ class, preferred term, and treatment group over the 16-week Treatment Period and the 4-week Follow-up Period.

Vital signs and safety laboratory test results will be listed and summarized by treatment group over the 16-week Treatment Period and the 4-week Follow-up Period. Summaries will be provided using descriptive statistics, including mean values and mean change from Baseline values, as well as numbers of subjects with values outside limits of the normal range at each time point.

Any CS physical examination findings and safety laboratory results will be summarized. ECG readings will be evaluated by the investigator and abnormalities, if present, will be summarized and listed.

The clinically noteworthy QT/QTc interval (> 450, > 480, or > 500 msec) or clinically noteworthy change from Baseline (> 30 or > 60 msec) will also be summarized using descriptive statistics.

Summary tables will be provided for concomitant medications initiated during the study period.

Pharmacokinetic Analysis

The PK analysis set will be used for the PK analysis. Trough plasma concentrations of ME3183 and its metabolite (CCI) will be summarized descriptively by treatment group in the tables, figures, and listings (TFL).

CCI

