### 6.2. Randomized Set

All subjects who have signed ICFs and have received a randomization number within the IWRS will be included in the randomized set.

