### 6.3. Safety Analysis Set

All randomized subjects who received at least 1 dose of study drug will be included in the safety analysis set. Analyses in the safety analysis set will be based on the study treatment actually received by each subject.

In the event of drug mis-dispensation, the following guidelines will be followed:

- For subjects randomized to the placebo group but received any active study drug, they will be included in the active treatment group corresponding to the largest number of kits dispensed.
- For subjects randomized to any one of the four active treatment groups, they will be included in the active treatment corresponding to the largest number of kits dispensed.

The Safety Analysis Set will be used for all analyses of safety endpoints.

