## 6.8. Protocol Deviations

All subject data will be reviewed for the occurrence of protocol deviations. Identified protocol deviations will be recorded into the Clinical Trial Management System (CTMS) by the Site Monitor. The detail on the types of Protocol deviation criteria is made in the BDRM Preparation Plan. Final decisions of subjects to be included in the PPS will be made at the BDRM. All deviations will be categorized as major or minor. Significant protocol deviations are defined as those with major severity.

Deviation type will be recorded as one of the following categories:

- Concomitant Medication / Administration of prohibited medication
- Inclusion or Exclusion Criteria
- Informed Consent / ICF not signed or signed late
- Informed Consent / Other
- Investigational Product / Incorrect IP kit given to subject
- Investigational Product / IP
- Investigational Product / IP Storage
- Investigational Product / Other
- Met Withdrawal Criteria but was not Withdrawn
- Randomization / Mis-stratification
- Randomization / Multiple Randomizations
- Randomization / Other
- Randomization / Randomized not Treated
- Randomization / Treated and not Randomized
- SAE not reported or reported late
- Study Procedure / Missed procedure

*This document is confidential.*

- Study Procedure / Other
- Study Procedure / Site Staff Authorization, Delegation, Training
- Study Procedure / Subject compliance
- Study Procedure / Unmasking (not per protocol)
- Study Procedure / Visit Missing
- Visit Window

This document is confidential.

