## 13. Safety

All safety analyses will be performed using the safety analysis set.

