## 20. Index of Listings

Listing Number	Name	Analysis Set
16.2.1.1	Subject Disposition	(Screened Set)
16.2.1.2	Screen Failures	(Screened Set)
16.2.2	Subjects with Any Protocol Deviations	(Screened Set)
16.2.3	Subjects Excluded from Analysis Sets	(Screened Set)
16.2.4.1	Demographics and Baseline Characteristics	(Full Analysis Set)
16.2.4.2	Baseline Disease Characteristics	(Full Analysis Set)
16.2.4.3	Medical History	(Full Analysis Set)
16.2.4.4.1	Prior and Concomitant Medications	(Full Analysis Set)
16.2.4.4.2	Prior and Concomitant Medical/Surgical Procedures	(Full Analysis Set)
16.2.4.4.3	Prior Systemic Treatment for Psoriasis	(Full Analysis Set)
16.2.5.1	Study Drug Administration	(Full Analysis Set)
16.2.5.2	Study Drug Compliance	(Full Analysis Set)
16.2.6.1	Psoriasis Area and Severity Index (PSAI)	(Full Analysis Set)
16.2.6.2	Static Physician's Global Assessment (sPGA)	(Full Analysis Set)
16.2.6.3	Dermatology Life Quality Index (DLQI)	(Full Analysis Set)
16.2.6.4	Body Surface Area (BSA)	(Full Analysis Set)
16.2.6.5	Numerical Rating Scale (NRS)	(Full Analysis Set)
16.2.7.1	Treatment-Emergent Adverse Events	(Full Analysis Set)
16.2.7.2	Non-Treatment-Emergent Adverse Events	(Full Analysis Set)
16.2.8.1.1	Laboratory Reference Ranges	
16.2.8.1.2	Hematology and Coagulation	(Full Analysis Set)
16.2.8.1.3	Blood Chemistry	(Full Analysis Set)
16.2.8.1.4	Urinalysis (Dipstick)	(Full Analysis Set)
16.2.8.2.1	Vital Signs	(Full Analysis Set)
16.2.8.2.2	Electrocardiogram (ECG)	(Full Analysis Set)
16.2.8.2.3	Physical Examination	(Full Analysis Set)
16.2.8.2.4	Serology at Screening	(Full Analysis Set)
16.2.8.2.5	Serum Pregnancy Test and FSH at Screening	(Full Analysis Set)
16.2.8.2.6	Urine Pregnancy Test	(Full Analysis Set)
16.2.8.2.7	Individual Ctrough Concentrations	(Full Analysis Set)
CCI		

This document is confidential.

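### The safety analysis set requires randomization as well as a dose, so a subject treated without being randomized would appear in no safety table and no adverse event, laboratory, vital-sign or ECG listing

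*Protocol*

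**What the plan says.** The definition is the same in the protocol synopsis, protocol 15.2 and SAP 6.3: "All randomized subjects who received at least 1 dose of study drug will be included in the safety analysis set". All three then analyse the set by the treatment each subject actually received.

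SAP 6.2 fixes what randomized means. It covers consented subjects who "have received a randomization number within the IWRS will be included in the randomized set".

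The set governs all safety output. SAP 6.3 states: "The Safety Analysis Set will be used for all analyses of safety endpoints". SAP 13 repeats it: "All safety analyses will be performed using the safety analysis set". In the SAP 18 index, every 14.3 table carries the Safety Analysis Set label.

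SAP 6.8 lists the types under which deviations are recorded. One is "Randomization / Treated and not Randomized", separate from the codes for randomized but untreated subjects and for multiple randomizations.

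SAP 6.3 also has two rules for mis-dispensed drug. One opens "For subjects randomized to the placebo group but received any active study drug", the other "For subjects randomized to any one of the four active treatment groups".

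The section 16.2 safety listings are not on the safety set. SAP 20 labels listing 16.2.7.1 "Treatment-Emergent Adverse Events (Full Analysis Set", and gives the same label to the laboratory, vital-sign and ECG listings. Under SAP 6.4 the FAS needs randomization, a dose, and an evaluable post-baseline time point for the primary endpoint.

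**The concern.** A safety set is meant to hold everyone exposed to study drug. Here it holds everyone exposed who also has a randomization number. For subjects with a number, the extra condition changes nothing. Its only effect is to remove exposed subjects without one, and the SAP has a code for exactly that status but does not say where their safety data go.

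An AE, a QTc outlier or a laboratory abnormality in such a subject would be missing from both numerator and denominator. Protocol 5.3 names QTc prolongation and arteritis as nonclinical findings, and protocol 5.4 says this is the first study in patients. With 25 subjects per arm, a single event is visible in a table.

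Protocol 15.4 also undertakes to list and tabulate every recorded AE and SAE, and SAP 13.1 to list all AEs by subject. For this subject the set labels in the indexes would prevent both.

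**Working it through.** The plan states no figure on this point, so the check follows one hypothetical subject, dosed with no IWRS randomization number, through the planned output.

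| Output | Set | Subject included? |
|---|---|---|
| 14.3 tables, including listings 14.3.2.1 (serious events) and 14.3.2.2 (events leading to discontinuation) | Safety Analysis Set | No: not randomized |
| Listings 16.2.7.1 and 16.2.7.2 (AEs) | FAS | No: not randomized |
| Listings 16.2.8.1.2 to 16.2.8.1.4 (laboratory), 16.2.8.2.1 (vital signs), 16.2.8.2.2 (ECG) | FAS | No: not randomized |
| Table 14.1.2.1 (major deviations), Table 14.1.2.2 (reasons for exclusion) | Randomized Set | No |
| Listings 16.2.1.1 (disposition), 16.2.2 (deviations), 16.2.3 (exclusions) | Screened Set | Yes, if consented |

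The subject would be visible only in Screened Set output on disposition, deviations and set membership. None of that output is planned to report AE, laboratory or ECG data. The mis-dispensation rules do not help, because both start from a subject's randomized group and this subject has none.

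**Size.** Inputs: 25 subjects per arm and 5 arms (protocol 7.1), so 5 × 25 = 125, which matches the planned total. Assumptions for illustration: all 25 in the arm are dosed, there is one extra treated subject who was never randomized, and that subject has one event. The subject is additional to the 25, so inclusion adds 1 to the denominator.

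- Arm with no other such event: 0/25 = 0% if omitted; 1/(25 + 1) = 1/26 = 3.85% if included.
- Arm with one event already: 1/25 = 4.00% if omitted; 2/26 = 7.69% if included.
- All arms together, no other event: 0/125 = 0% if omitted; 1/(125 + 1) = 1/126 = 0.79% if included.

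If no such subject exists, every table is unchanged.

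**The case against.** The strongest reply is that this is a wording gap for a hypothetical case. Under protocol 9.3.2 the pharmacist dispenses by a kit number from the IWRS, the system that also randomizes. Protocol 9.3.1 places assignment before Day 1 dosing. That control would have to be bypassed. This stands, and it keeps the point minor.

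A reader might infer from the SAP 6.8 code that the sponsor expects such subjects, or has had one. The documents do not support that. The list is a broad coding scheme that runs from storage to visit windows with several catch-all entries, and a code does not predict an event.

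A reader might also take the mis-dispensation text added in SAP version 1.1, or the incorrect-kit code, as evidence of unrandomized exposure. The added rules concern randomized subjects only. The incorrect-kit code need not involve anyone else.

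Nor would the subject be lost to the trial. AEs are recorded in the eCRF from consent (protocol 12.6). SAEs are reported from consent whether or not related to drug (protocol 12.6.4). Deviations go into the study report (protocol 16.7.2). SAP 8.1 says generally that all subject data will be listed, but the specific labels in SAP 20 put the AE listings on the FAS. The loss is from the planned safety tables and those listings.

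Finally, deleting one word would not be a full repair. It would leave no arm-assignment rule for this subject and would leave the listings on the FAS. That is correct, and the fix covers both.

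**Conclusion.** The point holds on the text as a low-cost improvement. The definitions agree with each other across the protocol and SAP, but the rule they share drops an exposed subject from the planned safety output in a situation for which the SAP keeps a code.

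The size depends on whether the case arises. With no such subject there is no effect. With one subject and one event, an arm shows 0% instead of 3.85%, or 4.00% instead of 7.69% where an event is already present, assuming 25 dosed subjects in that arm. It would be wrong to describe the omitted subject as 4% (1/25) of an arm, because a subject who was never randomized is not one of the 25. No efficacy comparison is affected.

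**What to change.** 1. In the protocol synopsis, protocol 15.2 and SAP 6.3, define the safety set as every subject who took at least one dose of study drug, analysed by treatment actually received. Protocol 15 lets the SAP prevail where the two differ, so a SAP change alone would take effect, with an entry in SAP 14.
2. In SAP 6.3, extend the existing largest-number-of-kits rule to treated subjects with no randomized group: to the active group with the most kits dispensed if any active drug was received, and to placebo if only placebo was received.
3. In SAP 20, move listings 16.2.7 and 16.2.8, other than the PK concentration listing, from the FAS to the safety analysis set.
4. Because the set would no longer be strictly a subset of randomized subjects, footnote the SAP 9.1 disposition percentages or show any such subject as a separate count.

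The cost is a few text edits and relabelled listings, with no extra data and little programming. If no such subject exists, the tables do not change. The moved listings would still gain any dosed subject who is outside the FAS for lack of an evaluable post-baseline time point.
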